The Effects of Dual Task Training on Motor and Non-Motor Function in Individuals with
Parkinson's Disease

NCT02538029

1.31.19

Statistical Analysis Plan

Phase 1:

Baseline participant demographics and outcome variables will be summarized by group using mean \pm standard deviation for normally distributed variables, median [25th percentile, 75th percentile] for data that is not normally distributed, or N (%) (categorical data). Paired sample t-tests will be used to detect differences in cognitive scores between single and dual-task conditions. A repeated measures analysis of variance (ANOVA) model will be used to determine the effects of the different cognitive dual tasks and single-task on gait performance as measured by the spatial-temporal parameters of gait. When the ANOVA model results in significant differences in comparison from single to dual-task, a post hoc pairwise comparison will be performed to identify which tasks were significantly different from each other. The p-values in multiple comparisons will be adjusted using the Bonferroni correction. All statistical testing will be performed at the 5% level of significance.

Phase 2:

Baseline participant demographics and outcome variables will be summarized by group using mean \pm standard deviation for normally distributed variables, median [25th percentile, 75th percentile] for data that is not normally distributed, or N (%) (categorical data). The intervention effects on outcomes will be assessed using separate linear mixed effects models, each including a random intercept, main effects for group, time, and a group-by-time interaction term. Given a significant group by time interaction, post hoc pairwise comparisons will be performed between groups at each follow-up. In the absence of a group-by-time interaction, the overall change across collapsed groups between each evaluation will be estimated (i.e., change from Baseline to End of Treatment and Baseline to End of Treatment + 4 weeks). All comparisons will be performed at the 0.05 significance level. Within each outcome, pairwise comparisons will be Bonferroni corrected to maintain a 5% type I error rate per outcome.

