### **Specific Aims:**

#### **Aim 1: To categorize gait and balance deficits during DT constructs in individuals with PD.**

A three-dimensional (3-D) gait analysis using the CAREN system will be used during ST (walking alone) and DT conditions which consist of walking and completing tasks in the following cognitive domains: processing speed, visual memory, verbal memory, executive function, and attention (See Table 1 for cognitive tasks). Specifically, the CAREN gait analysis will examine spatiotemporal parameters of gait along with gait variability and joint angles. Additionally, a limit of stability (LOS) test will be conducted during ST and DT conditions.

*Hypothesis:* Gait parameters and LOS will be impaired under DT conditions compared to ST.

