#### **Aim 2: To create and pilot a DT clinical intervention based on biomechanical analysis from the CAREN system that improves motor and non-motor function of individuals with PD.**

Primary motor outcome will include a 3-D gait analysis using the same parameters as stated in Aim 1. Secondary clinical motor outcome include distance walked during the 2 Minute Walk Test (2MWT) under ST and DT conditions. The Quality of Life in Neurological Disorders (Neuro-QOL) questionnaire will be administered as a quality of life measure. Fall risk will be assessed through the Activities-specific Balance Confidence (ABC) Scale. Cognitive measures, motor, and non-motor tests are described in Table 1.

*Hypothesis:* The DT clinical group will demonstrate the greater improvements in motor and non-motor function compared to the ST groups.

**Research Plan:** A total of 15 individuals diagnosed with idiopathic PD will be included in the initial gait analysis to categorize gait and postural control deficits associated with DT constructs (Figure 2). During Phase 1, all interventions will be carefully documented in order to attribute changes in gait parameters of postural stability with a domain of cognitive function. Phase 2 of the study (N=20) will randomize participants into two groups: 1) DT clinical and 2) ST (Figure 2). *Both groups will receive a time-matched intervention, 3x/week for a total of 8 weeks.* If an individual misses a session, he/she will be required to make it up on a different day of the same week or at the end in order for all 24 sessions to be complete. The entire intervention must be completed within a 10 week period. Intervention sessions for all groups will be completed under the guidance of a physical or occupational therapist who specializes in neurological rehabilitation. Outcome measures for Phase 2 will be administered at baseline, end of treatment (EOT), and EOT+4 weeks (EOT+4) by a blinded evaluator. The purpose of the EOT+4 testing is to gauge the permanence of the training intervention. All participants will be asked to wear a wrist-worn activity monitor that will measure steps/day throughout the duration of Phase 2 participation (baseline through EOT+4).

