**Expected Results:** We anticipate that both DT and ST groups will improve motor and cognitive constructs in ST conditions. It is anticipated that the DT clinical group will improve compared to the ST group in both motor and cognitive performance during DT conditions, quality of life, and fall risk. We do not anticipate that DT constructs will change as a result of ST training due to specificity of training. We anticipate that one of the hallmark findings of this study will be insight to which DT constructs result in specific gait and postural control changes. This will guide clinicians in selecting the most appropriate interventions for individuals with PD, and we anticipate this to be the most important findings of this study to guide future research and clinical decisions.

**Participant Screening:** Participants will be pre-screened by the study coordinator. The following inclusion/exclusion criteria will be used:

Inclusion Criteria:

1. Clinical diagnosis of idiopathic PD
2. Able to provide informed consent
3. Ability to ambulate  $\geq 300$ ft with or without an assistive device
4. Hoehn and Yahr stage 2-4
5.  $\geq 2$  fall related to PD in the past 12 months

Exclusion Criteria:

1. Undergone any surgical procedure for the treatment of PD, such as deep brain stimulation
2. Those who have more than 2 uncontrolled cardiovascular risk factors (uncontrolled heart disease, uncontrolled diabetes, etc.) that would qualify them as a high risk exerciser
3. Musculoskeletal injury or neurological injury other than PD that would restrict physical activity
4. Inability to follow 2 step commands
5. Significant cognitive impairment as designated by  $\geq 3$  errors on the Short Portable Mental Status Questionnaire

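### The Phase 1 repeated measures ANOVA has no rule for an unusable walking condition; in its classical form one missing walk removes the participant, which would understate dual-task deficits if loss is related to severity

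*SAP*

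**What the plan says.** The Protocol's Research Plan sets the size of Phase 1: "A total of 15 individuals diagnosed with idiopathic PD will be included in the initial gait analysis". Aim 1 has them walk alone and while doing tasks in five cognitive domains: "processing speed, visual memory, verbal memory, executive function, and attention (See Table 1 for cognitive tasks"). Table 1 also lists five cognitive tasks. That makes about six walking conditions per person.

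The SAP, Phase 1, analyses the spatiotemporal gait parameters as follows: "A repeated measures analysis of variance (ANOVA) model will be used to determine the effects of the different cognitive dual tasks", with single-task walking as a further condition. Post hoc pairs follow a significant result: "The p-values in multiple comparisons will be adjusted using the Bonferroni correction". The level is 5%.

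For Phase 2 the same SAP names a different tool: "separate linear mixed effects models, each including a random intercept".

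Neither document gives Phase 1 a missing-data rule, an analysis set, or a rule for a walk that is stopped early. The make-up rules in the Protocol concern Phase 2 training sessions. Table 1 has no outcome that counts an unfinished condition.

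**The concern.** A classical repeated measures ANOVA compares conditions within people who have all of them. One missing condition out of six removes the other five as well, single-task walking included. Because the SAP names mixed models for Phase 2 and not for Phase 1, the classical form is the natural reading of Phase 1.

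The population makes it plausible that some walks will be unusable and that this will be related to severity. Entry allows "Hoehn and Yahr stage 2-4", permits an assistive device and requires at least two PD-related falls in the past 12 months (Protocol, Participant Screening). The Protocol's rationale links dual tasking to loss of balance and falls. If the people lost are those with the larger deficits, the analysis that is meant to describe the deficit is run on the milder part of the sample.

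The Phase 1 result is meant to be used. Observations are documented "in order to attribute changes in gait parameters of postural stability with a domain of cognitive function", and the gait findings are to set priorities for the Phase 2 intervention.

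**Working it through.** The documents give no effect size, SD or non-completion figure for Phase 1, so there is no figure of the plan to reproduce. Every loss rate below is an assumption.

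**1. How quickly complete rows are lost.** Let *p* be the chance that one dual-task walk is unusable, independent across walks, with five such walks for each of 15 people (75 in all).

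- Expected complete participants = 15 × (1 − *p*)^5
- Chance of losing at least one participant = 1 − (1 − *p*)^75

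| *p* | Expected complete of 15 | Chance of losing at least one |
|---|---|---|
| 1% | 14.3 | 53% |
| 2% | 13.6 | 78% |
| 5% | 11.6 | 98% |
| 10% | 8.9 | about 100% |

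The classical error degrees of freedom are (n − 1) × (6 − 1): 70 with all 15 people, and 65, 60, 55 and 50 with one to four people dropped. This is the cost in precision, whatever the reason for the loss.

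**2. Bias when loss depends on severity.** Simulation: 15 people, five dual-task conditions, person/residual SDs of 1/0.5 and of 0.7/0.7 (total SD of a deficit about 1), and probability of losing a walk = logistic(*a* + deficit). The odds of loss thus rise e-fold per unit of deficit. The value of *a* sets the overall loss rate. Bias is downward, in deficit SDs, and the ranges cover the two SD settings.

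| Condition-walks lost | Complete of 15 | Complete-case bias | Mixed-model bias |
|---|---|---|---|
| about 1% (*a* = −5) | about 14.2 | 0.04–0.06 | under 0.01 |
| 4–5% (*a* = −3.5) | about 12 | 0.11–0.20 | 0.01–0.03 |
| about 7% (*a* = −3) | about 10.7 | 0.17–0.28 | 0.02–0.04 |
| about 11% (*a* = −2.5) | about 9 | 0.25–0.38 | 0.04–0.06 |

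Repeat runs moved the figures by 0.01 to 0.02; the lower end of the first row fell between 0.02 and 0.04. The run-to-run SD of the estimate in that row is about 0.20 to 0.27, so the bias there is small beside sampling error.

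**3. A second model, as a cross-check.** Assumed: mean dual-task cost 0.5, between-person SD of cost 0.4, residual SD 0.3, baseline SD 1, and 300 runs per scenario. The *k* people with the largest cost each miss only their worst dual-task walk.

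| *k* | Full data | Complete cases | Mixed model | Complete-case shortfall |
|---|---|---|---|---|
| 1 | 0.507 | 0.454 | 0.499 | 0.053/0.507 = 10% |
| 2 | 0.496 | 0.409 | 0.481 | 0.087/0.496 = 18% |
| 3 | 0.511 | 0.379 | 0.489 | 0.132/0.511 = 26% |
| 4 | 0.483 | 0.312 | 0.455 | 0.171/0.483 = 35% |

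The mixed-model shortfall is 0.008/0.507 = 2% at *k* = 1 and 0.028/0.483 = 6% at *k* = 4.

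When the *k* people are chosen at random, the complete-case estimate shows no bias (for *k* = 4, 0.494 against 0.491). The mixed model is then slightly low (0.469), because each missing walk is still that person's worst. The mixed model therefore removes most of the attenuation when severity drives the loss, but not the part caused by the unseen poor walk itself.

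**The case against.** The strongest reply is that the SAP never states listwise deletion. It names no software and no complete-case rule, and a repeated measures model can be fitted in mixed-model software that keeps partial rows. This stands: what the documents show is a missing rule together with a natural reading, not a declared exclusion.

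A reader might also infer that the worst-affected participants will leave the analysis. The documents do not support that. They give no walk duration, no non-completion rate and no relation between stopping and severity. Several entry and test conditions limit impairment: the ability to walk at least 300 ft, exclusion for three or more errors on the mental status questionnaire or for inability to follow two-step commands, and testing on prescribed PD medication.

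Nor does every difficulty lose gait data. If the participant abandons the cognitive task, the gait is still recorded, and the lapse can show in the cognitive scores, which Phase 1 compares by paired t-test. The harness is worn by design in the VR setting, so relying on it does not void a walk. A shortened walk may still give usable strides. Only a walk with none is missing.

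Finally, with complete data both methods give the same condition means, and Phase 1 is a one-group characterisation of 15 people. That limits the consequence. It does not remove the case for naming a method that copes with a missing walk, since doing so costs little.

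**Conclusion.** The point holds in conditional form. The SAP leaves an unusable Phase 1 walk without a rule and names a method whose classical form discards the whole participant. Understatement of the dual-task deficit follows only if three things are true: some walks are unusable, their loss is related to severity, and complete cases are analysed. Under the assumed loss model the size runs from negligible at about 1% of walks lost to 0.25–0.38 SD at about 11%, against at most about 0.06 SD for a mixed model. If loss is unrelated to severity there is no complete-case bias, only fewer people and fewer error degrees of freedom.

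A reader might go further and infer that the bias is worst for the hardest tasks and distorts the choice of Phase 2 tasks. That is not shown. The first simulation gives all five tasks the same loss model, both report only the overall mean deficit, and neither examines the ranking of tasks.

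**What to change.** In SAP Phase 1, replace the repeated measures ANOVA with a linear mixed model: condition as fixed effect, participant as random effect, and a small-sample degrees-of-freedom correction such as Kenward-Roger. State that it uses every usable condition from all 15 participants, including usable strides from shortened walks, and define what counts as usable. Keep the Bonferroni-adjusted pairwise comparisons.

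Record for each condition whether the walk was finished and, if not, why. Report the number and reasons by condition beside the gait parameters. This is needed because the mixed model does not fully correct loss caused by the unobserved poor performance itself.

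The cost is SAP wording, one data field, a degrees-of-freedom approximation and a stated covariance assumption. If every walk is usable, the condition means do not change.

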surface, uneven surfaces) or cognitive demands (e.g. memory, attention, executive function) in a safe environment. The CAREN system is unique from other experimental environments due to the ability to create real-world environments (e.g. street scene with pedestrian and vehicle traffic, trail walking) in which the motor and cognitive aspects of function can be systematically manipulated and measured.

One of the greatest barriers to DT training is the lack of knowledge about effective clinical interventions. The clear benefit to this highly-advanced system is opportunity to investigate mechanisms of dual tasking deficits in a given environment. For example, if participants with PD exhibit increased step variability and decreased stride length during visual memory cognitive tasks that are not seen during verbal memory cognitive tasks, this would provide valuable insight into task selection during a clinical intervention.

**The primary aim of the proposed project is to characterize DT deficits to improve motor, cognitive, and quality of life outcomes in individuals with PD.** A single center study is outlined in Figure 2. Phase 1 of the intervention will involve an in-depth gait analysis on 15 individuals with PD. The purpose of Phase 1 is to generalize characteristics of gait and postural control during specific DT conditions, as in the example provided above. Phase 2 (N=20) involves the clinical translation of these findings. This phase will involve creating a clinical intervention based on the objective information gathered from the CAREN system. Researchers will use the biomechanical data gathered from the CAREN system to prioritize interventions based on given gait and postural control deviations during DT interventions. To continue with the above example, if we find that visual memory tasks lead to decreased stride length, then the therapeutic intervention would be a task such as targeted stepping during gait (e.g. placing stickers slightly wider than normal step length on a treadmill) while performing various visual memory tasks. The intervention will take place 3x/week for a total of 8 weeks. Interventional groups will include: 1) DT clinical group (N=10) and 2) Single task group (N=10). ST training will serve as a control group.

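### SAP Phase 1 makes the gait comparisons conditional on a significant ANOVA, although Bonferroni already controls their error, and names no direct single- versus dual-task test of the Aim 1 hypothesis

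*SAP*

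**What the plan says.** The Aim 1 hypothesis in the Protocol (Specific Aims) is directional and compares single-task (ST) with dual-task (DT) walking: "Gait parameters and LOS will be impaired under DT conditions compared to ST". The dual tasks cover five cognitive domains: "processing speed, visual memory, verbal memory, executive function, and attention". Phase 1 is an "in-depth gait analysis on 15 individuals with PD".

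For gait, the Phase 1 section of the SAP fits one repeated-measures ANOVA "to determine the effects of the different cognitive dual tasks and single-task on gait performance". It then states: "When the ANOVA model results in significant differences in comparison from single to dual-task, a post hoc pairwise comparison will be performed". The purpose of that second step is "to identify which tasks were significantly different from each other". On multiplicity it says: "The p-values in multiple comparisons will be adjusted using the Bonferroni correction". On the error level it says: "All statistical testing will be performed at the 5% level of significance".

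The SAP names no planned single-versus-dual contrast for gait. Cognitive scores, by contrast, are compared between single- and dual-task by paired t-tests with no preceding condition.

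**The concern.** On the natural reading, the condition is the ANOVA's overall test of condition. Its null hypothesis is that no two conditions differ, which is not the Aim 1 statement. Two consequences follow.

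- **Redundant condition.** A Bonferroni-adjusted family needs no preliminary test to hold its error rate. Requiring a significant F first cannot make any adjusted comparison more likely to succeed and will sometimes block one that would have succeeded.
- **Mismatch with the hypothesis.** The F-test can be significant because the dual tasks differ among themselves, with no average difference from walking alone. It also spreads a deficit common to all dual tasks over five degrees of freedom.

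At stake is whether the direct answer to the Aim 1 gait hypothesis is reported at all, in a phase with 15 participants.

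**Working it through.** The plan gives no Phase 1 power, effect size or variance, so there is no figure to reproduce.

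**Inputs from the documents.** n = 15 (Protocol, Rationale and Impact). Level 5% (SAP). Conditions: walking alone plus five dual-task domains (Aim 1; Table 1 also lists five concurrent tasks), so k = 6. The SAP does not state the number of levels; six is inferred.

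**Assumptions.** Two-sided tests, normal data, equal within-person error SD and one gait parameter. The shift d is the dual-task deficit in units of that error SD.

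**Family-wise error without the condition.** The Bonferroni bound for five single-versus-dual pairs is 5 × 0.01 = 0.05. Simulated under the global null at n = 15, it is 4.2%. With the F-test required first it falls to 1.8%.

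**Omnibus F against a direct contrast, equal deficit in all five dual tasks.** The condition means have squared deviations summing to d²(25/36 + 5/36) = (5/6)d², so the noncentrality is λ = 15 × d² × 5/6.

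- d = 0.6: λ = 4.5
- d = 0.7: λ = 6.125
- d = 0.8: λ = 8.0

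The omnibus test refers this to F(5,70). The contrast of single-task with the dual-task mean refers the same λ to F(1,14).

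| d | Omnibus F | Contrast |
|---|---|---|
| 0.6 | 30% | 51% |
| 0.7 | 41% | 63% |
| 0.8 | 53% | 75% |

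**Cost of the condition itself.** This is the probability that at least one single-versus-dual pair is significant after Bonferroni (simulated, equal deficit).

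| d | 5 pairs, F required | 5 pairs, no condition | 15 pairs, F required | 15 pairs, no condition |
|---|---|---|---|---|
| 0.6 | 26% | 38% | 18% | 22% |
| 0.7 | 36% | 49% | 27% | 30% |
| 0.8 | 48% | 61% | 37% | 41% |

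The condition costs 12 to 13 points with five pairs and about 4 (3 to 4 as rounded) with all 6 × 5/2 = 15 pairs. Without the condition, going from 15 pairs to five adds 16 to 20 points (22% to 38%, 30% to 49%, 41% to 61%), so on the 15-pair reading the size of the family costs more than the condition.

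**When deficits are not equal (five pairs).**

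- Deficits from 0.42 to 0.99 SD across tasks: 51% with the condition, 60% without.
- One affected task at 1.05 SD: 48% with, 50% without.
- Dual-task costs varying between people, with half of the variance of the single-minus-dual difference shared by all dual tasks, a mean difference of 0.5 SD of that difference, and a Greenhouse-Geisser-corrected F: 36% with, 40% without.

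**What a significant F means.** Let the five dual tasks lie at +0.5, −0.5, +0.25, −0.25 and 0 error SD from single-task, so that their average equals single-task. The F-test rejects in 61% of simulated trials and the contrast in 5%.

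**Where the contrast is not better.**

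- Mean shift 0.7, mildly unequal deficits (0.42 to 0.98): omnibus 59%, contrast 63%.
- Mean shift 0.7, clearly unequal deficits (0.14 to 1.26): omnibus 90%, contrast 64%.
- Shift 0.7, between-person SD of dual-task cost 1.0: omnibus 34%, contrast 39%.
- One task only at 1.05 SD: contrast 11%, against 50% for the unconditional five pairs.

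**The case against.** The case for the plan has four parts.

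1. **The condition may not be the omnibus test.** It refers to differences from single to dual-task, so a single-versus-dual test within the model could be meant. This stands as an ambiguity. But no such test is described, and if one was intended the SAP should name it.
2. **Aim 1 is wider than its hypothesis sentence.** The Protocol wants deficits categorised by cognitive domain, gives a visual-versus-verbal-memory example and treats task-specific findings as a main product. A test sensitive to differences among dual tasks serves that purpose. This stands, and is why the F-test should be kept for that question and the averaged contrast should not be the only Aim 1 test.
3. **An omnibus test followed by adjusted pairs is conventional and valid** in a small exploratory phase. True. The condition also lowers family-wise error further, from 4.2% to 1.8%, but the family is already below 5%, so this extra protection is not needed.
4. **The large power gap depends on the scenario.** Also true, as the unequal-deficit results show.

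A reader might infer that the plan will miss a dual-task deficit far more often than necessary. The documents do not support that in general: they give no effect size or variance, the 20 to 22 point omnibus-versus-contrast gap needs much the same deficit in every task, and the gap reverses for clearly task-specific deficits. A reader might also infer that a non-significant F would deprive Phase 2 of its training content. The Protocol says the biomechanical data will be used to prioritise interventions and states no significance rule for doing so.

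**Conclusion.** The point holds in a limited form. The SAP makes Bonferroni-adjusted gait comparisons depend on a preliminary test they do not need, and it names no direct gait test of the single-versus-dual hypothesis. If the condition is the omnibus F, removing it never lowers power and keeps family-wise error within 5%. The gain for an equal deficit of 0.6 to 0.8 error SD is about 12 points with five pairs and about 4 with 15. It is smaller when deficits differ by task or costs vary widely between people. Separately, a significant F should not be read as support for Aim 1, since it can arise with no average dual-task deficit. All sizes rest on six conditions, equal within-person error SD and two-sided 5% tests for one gait parameter. This is an inexpensive improvement to the plan; the planned analysis is not invalid.

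**What to change.** In SAP Phase 1:

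1. Delete the clause that makes the pairwise step depend on a significant ANOVA. State that, for each gait parameter, the five comparisons of single-task with each dual task will be reported with Bonferroni adjustment over five and with confidence intervals, whatever the F-test shows.
2. Keep the ANOVA F-test for differences among the dual tasks, and say that it is not the test of the Aim 1 hypothesis.
3. Optionally, pre-specify the 1-df within-person contrast of single-task with the mean of the dual tasks, with its 95% confidence interval, as the test of the overall hypothesis. It should be read alongside the per-task comparisons and not in place of them: it is stronger when the deficit is broadly common (63% against 41% for the omnibus F at 0.7 SD) and weak when one task drives the effect (11%).

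The cost is two or three sentences and no new data. The contrast does not identify tasks, and the contrast, the five pairs and any comparisons among dual tasks should be declared as separate families, so that the 5% level is understood to apply within each.

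### As most plainly read, the Phase 2 follow-up to a significant interaction compares group levels and makes no use of baseline; the step is valid, but materially less precise than a baseline-adjusted comparison if the baseline to follow-up correlation is about 0.5 or more

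*SAP*

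**What the plan says.** The SAP (Phase 2) fits a separate linear mixed model to each outcome, "each including a random intercept, main effects for group, time, and a group-by-time interaction term". It lists no baseline covariate. Baseline appears to enter as one of the response times, because the SAP later estimates change from it.

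If the interaction is significant, the next step is: "Given a significant group by time interaction, post hoc pairwise comparisons will be performed between groups at each follow-up". If it is not, the SAP turns to pooled change: "In the absence of a group-by-time interaction, the overall change across collapsed groups between each evaluation will be estimated". That second sentence goes on to name the changes from baseline to each follow-up; the first does not mention change. On multiplicity: "Within each outcome, pairwise comparisons will be Bonferroni corrected to maintain a 5% type I error rate per outcome".

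The protocol describes Phase 2 as a pilot (Aim 2: "To create and pilot a DT clinical intervention based on biomechanical analysis from the CAREN system") with 10 participants per arm (Rationale and Impact). The Aim 2 hypothesis concerns improvement: "The DT clinical group will demonstrate the greater improvements in motor and non-motor function compared to the ST groups". The Research Plan schedules the assessments, "Outcome measures for Phase 2 will be administered at baseline, end of treatment (EOT), and EOT+4 weeks (EOT+4) by a blinded evaluator", and gives the reason for the last one: "The purpose of the EOT+4 testing is to gauge the permanence of the training intervention".

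**The concern.** The interaction test has 2 degrees of freedom. It answers whether the arms change differently, which is what Aim 2 asks, but it gives no direction, size or timing. The step the SAP names for describing those is the between-group comparison at each follow-up, and the EOT+4 comparison is where permanence would be judged.

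If that step compares levels, it answers a slightly different question from the test that opened it. A level difference at follow-up is the difference in change plus whatever difference the arms happened to have at baseline. With 10 per arm that chance component is not small, and the baseline value that could remove it has already been collected. At stake are the precision of the reported effect and its agreement with the interaction test. Validity is not at stake.

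**Working it through.** **Inputs from the documents.** 10 per arm and two randomised arms (Protocol, Rationale and Impact; Research Plan); baseline, EOT and EOT+4 (Research Plan); random-intercept model, 0.05 for the interaction, Bonferroni within outcome (SAP, Phase 2). The documents give no effect size, SD or correlation, so there is no stated figure to reproduce.

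**Assumptions.** SD = 1 at each visit; equal correlation r between visits, as a random intercept implies; complete data; two-sided tests; two post hoc comparisons at 0.05/2 = 0.025 each. r is ranged over 0.3, 0.5, 0.7 and 0.8.

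**Step 1: does the level contrast use baseline?** In one complete-data example fitted with the planned model, the group contrast at EOT was 1.200, equal to the raw difference in EOT means. The baseline difference was -0.122 and the interaction coefficient was 1.200 - (-0.122) = 1.322. With complete data, then, the level contrast makes no use of baseline, while the difference in change is already in the model's coefficients.

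**Step 2: chance imbalance.** The SE of the baseline difference is sqrt(2/10) = 0.447 SD. P(|Z| > 0.5/0.447) = 0.264, so 26% of trials have arms more than 0.5 SD apart at baseline on a given outcome.

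**Step 3: precision.**
- Level: sqrt(2/10) = 0.447 at every r.
- Difference in change: sqrt(4(1 - r)/10).
- ANCOVA at one visit: sqrt(0.2(1 - r²)(1 + 1/16)). At r = 0.5 this is sqrt(0.2 × 0.75 × 1.0625) = 0.399.
- Common-baseline mixed model (one baseline mean for both arms): by simulation.

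| | r = 0.3 | 0.5 | 0.7 | 0.8 |
|---|---|---|---|---|
| SE, level | 0.447 | 0.447 | 0.447 | 0.447 |
| SE, ANCOVA | 0.440 | 0.399 | 0.329 | 0.277 |
| SE, common baseline | 0.435 | 0.392 | 0.323 | 0.271 |
| SE, change | 0.529 | 0.447 | 0.346 | 0.283 |
| Mean 97.5% half-width, level | 1.03 | 1.04 | 1.05 | 1.06 |
| Half-width, ANCOVA | 1.06 | 0.96 | 0.80 | 0.67 |
| Half-width, common baseline | 0.98 | 0.89 | 0.74 | 0.62 |
| Half-width, change | 1.23 | 1.04 | 0.80 | 0.66 |

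The variance saving of ANCOVA over level is 1 - (1 - r²)(17/16) = 3% / 20% / 46% / 62%. At r = 0.3 its interval is nevertheless slightly wider (1.06 against 1.03), because it has 17 residual df and the level contrast from the mixed model has about 45. The level df fall to about 37, 28 and 24 at r = 0.5, 0.7 and 0.8. Change beats level only when 4(1 - r)/10 < 2/10, that is, r > 0.5.

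**Step 4: agreement with the interaction test.** Simulation of 40,000 trials per setting, interaction F test at 0.05, then each contrast at EOT and EOT+4 at 0.025. With an assumed 0.8 SD effect at both visits the interaction is significant in about 31% / 41% / 63% / 81% of trials. Among those, neither visit shows a significant group difference in:

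| | r = 0.3 | 0.5 | 0.7 | 0.8 |
|---|---|---|---|---|
| Level | 29% | 41% | 53% | 60% |
| ANCOVA | 18% | 13% | 8% | 5% |
| Common baseline | 11% | 8% | 4% | 2% |
| Change | 3% | 2% | 1% | 1% |

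The level figures depend strongly on the assumed effect: 54/66/77/82% at 0.4 SD, 9/17/25/29% at 1.2 SD and 3/6/10/12% at 1.5 SD. They also depend on the threshold: at 0.05 per visit and 0.8 SD they are 18/28/41/47%.

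**Step 5: validity.** With no true effect, a significant interaction followed by a declared level difference occurs in 1.3/0.9/0.6/0.5% of trials. The mean level estimate under a 0.8 SD effect is 0.80 at every r.

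**The case against.** The strongest reply is that the SAP never says levels are compared. A comparison of changes at each follow-up would fit the wording; the disagreement would then be 1 to 3% in the 0.8 SD setting, and the precision comparison would be different. This stands. The level reading rests on the absence of any baseline term and on change being named only in the other branch. If change was meant, the sentence should say so.

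Second, a reader might infer that the comparison is biased, that it inflates false positives, or that Aim 2 goes untested. The documents support none of these. Randomisation makes the level contrast unbiased, Step 5 shows no inflation, and the planned interaction is a test of differential improvement.

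Third, a reader might infer that levels are always the less precise choice. They are not: below r = 0.5 they beat a difference in change, and near r = 0.3 they match or slightly beat ANCOVA at each visit.

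Fourth, two partial safeguards exist. The SAP summarises baseline outcomes by group, so an imbalance would be visible, though not adjusted for. The Bonferroni family is also largely fixed by two arms and two follow-ups; stating the number would help, but it is not a real gap.

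Finally, disagreement between two tests of different contrasts is not in itself an error, and its rate rests on an assumed effect. That is also right, and no single row of the table should be quoted without its assumptions.

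**Conclusion.** The point holds as a minor matter of precision and clear reporting in a 20-person pilot. On the plain but inferred reading, the post hoc step leaves out the collected baseline and carries any chance difference in it.

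The precision lost depends on r, which the documents do not give. Against baseline adjustment it is negligible near 0.3 and material from about 0.5, where ANCOVA saves 20% of the variance, rising to 62% at 0.8. Against a difference in change there is a loss only above 0.5.

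The step can also leave a significant interaction with no group difference to report, in roughly 29% to 60% of significant interactions under the 0.8 SD assumption and the range of r used. All figures assume complete data and equal correlations between visits; with missing visits the mixed model would recover some baseline information.

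**What to change.** Keep the interaction test as the gate. Then state in the SAP what is compared at EOT and EOT+4, that the two comparisons are tested at 0.025 each, and that confidence intervals will be reported. Two definitions are reasonable:

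- **Baseline-adjusted DT-minus-ST difference at each visit.** Use either the mixed model refitted with a common baseline mean, or an ANCOVA at each visit with baseline as covariate. Do not add baseline as a covariate to the gate model, where it is already a response. The common-baseline model is the more precise when correlations between visits are equal; ANCOVA does not rely on that. The cost is one extra fit per outcome, or one per visit for ANCOVA. ANCOVA also has 17 residual df where the level contrast has about 24 to 45, which slightly widens intervals when the correlation is low.
- **Between-group difference in change, from the planned model.** This needs wording only and agrees most closely with the gate, but it is less precise than levels when r is below 0.5. It also leans on the equal-correlation assumption: with assumed correlations of 0.6 (baseline to EOT), 0.5 (baseline to EOT+4) and 0.8 (EOT to EOT+4) and no true effect, the gate passed in 5.9% of simulated trials and a difference in change was declared in 5.7%, against 2.4% for ANCOVA.

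Neither option needs new data.
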